To compare two loading protocols using the new implant (NobelParallel™ CC) in posterior healed sites in two treatment arms: one in which the implant will be immediately provisionalized at the time of surgery, and another where the provisional crown will be delivered 3 months after the surgical procedure.

STUDY DESIGN AND STATISTICAL PROCEDURES OVERVIEW

This is a non-inferiority study of 12-month duration comparing the two treatment arms described above. Eligible patients with edentulous spaces at the maxillary or mandibular premolar/molar areas will be randomized to either an immediate provisionalization or a delayed provisionalization treatment arm. Patients in both treatment arms will receive their final fixed restoration at 4 months after surgery. The primary outcome of the study will be the radiographically assessed alveolar bone level change at the mesial and distal surface of the implant at 6 and 12 months after surgical placement. Secondary outcomes will include implant survival,

volumetric soft tissue changes, peri-implant probing depth, and implant stability by resonance frequency analysis.

POWER CALCULATIONS AND STATISTICAL ANALYSIS

Determination of sample size was based on anticipated differences in the primary outcome between the two treatment arms at 6 months (change in alveolar level from the time of implant placement). Based on similar data published in the literature (Esposito et al., 2013), we calculated with 1 mm bone remodeling in one treatment arm, and 1.5 mm bone remodeling in the second arm (i.e., expected mean difference between the two arms amounting to 0.5 mm). With a common standard deviation in both arms of 0.6 mm, the two-tailed effect size for a Student t-test (Cohen's d) amounts to 0.8333 mm. For an alpha error of 0.05 and power of 0.80, a total of 48 individuals in both arms is required for a two-tailed hypothesis. Thus, our plan is to enroll 50 individuals into the study.

Differences in the primary and secondary outcomes between the two treatment arms will be calculated using t-test for unmatched samples, after checking for data normality. Additional analyses will include regression models in which insertion torque (a measure of primary implant stability at the time of surgical placement) will be also used as a covariate along with treatment group allocation.

STUDY PROCEDURES

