At four months after implant surgery, patients in both arms will have a final fixture level impression according to standard protocol for fabrication of the final implant supported restoration (a full contour Zirconia abutment crown with an angulated screw channel), which will be delivered approximately 2 weeks later. Resonance frequency analysis measurements will be obtained to determine implant stability using an Ostell™ device. After delivery of the final restoration, a periapical radiograph will be obtained, soft tissue margin measurements will be carried out as described above, and peri-implant probing depths will be assessed at the same six sites. An alginate impression will also be obtained to produce a stone cast to be used in volumetric measurements.

At seven months after implant surgery, patients in both treatment groups will return for a follow up visit to reinforce oral hygiene and will receive oral prophylaxis.

At twelve months after implant surgery, patients in both treatment groups will return for a follow up visit to reinforce oral hygiene and to receive oral prophylaxis. Resonance frequency analysis measurements will be obtained to determine implant stability using an Ostell™ device. A periapical radiograph will be obtained, soft tissue margin measurements will be carried out as described above, and probing depths will be assessed at the same six sites around the implant. An impression will be obtained to produce a cast to be used in volumetric measurements. The 12-month examination will conclude the study visits.

Research procedures

1. Radiographic measurements of alveolar bone level mesial and distal to the implant (at baseline, four months and 12 months) will be carried out using the MIPACS software. The implant platform will be the reference point. Note that although the measurements will be carried out for the purposes of the study, periapical radiographs after completed surgery, at the time of delivery of the final restoration, and at 12-months post-surgery are standard protocol in implant dentistry. Thus, the study does not require any additional exposure to radiation beyond what is considered the standard of care.

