2. Measurements of soft tissue margin from a vacuum-formed stent at 6 sites per tooth (obtained at the day the provisional crown is delivered, i.e. at the post-operative visit 1-2 weeks after implant placement in the one-stage treatment arm, or at the post-operative visit 1-2 weeks after implant uncovering in the two-stage arm).
3. Probing depth measurements around the implant (at 4 and 12 months).
4. Volumetric assessments, based on digitally super-imposed casts (obtained at screening, 4 months and 12 months).
5. Resonance frequency analysis measurements using a Ostell™ device (at 4 and 12 months). These are non-invasive measurements of implant stability.

STUDY DRUGS

N/A

STUDY INSTRUMENTS

The NobelParallel™ CC implant is a new implant that has the same titanium oxide surface coating (TiUnite®) and a parallel-wall body design similar to the NobelSpeedy groovy™ and a conical internal connection. Both the implant and its prosthetic components have regulatory clearance [510(k)] by the Food and Drug Administration.

ADDITIONAL DATA COLLECTION

We will collect and review standard medical and dental history forms to confirm eligibility (age 18 years or older, participants who are systemically healthy or have controlled common systemic conditions, not pregnant, non-smoking or smoking <10 cigarettes/day, have no parafunctions or excessive occlusal forces, are not currently under orthodontic therapy, and have a stable occlusion). Intraoral photographs will be obtained for documentation purposes.

STUDY SUBJECTS

We will recruit 50 subjects among those referred to the College of Dental Medicine for tooth replacement using a dental implant in a posterior maxillary or mandibular region (premolar/molar area).

ADDITIONAL INCLUSION CRITERIA

Age 18 or older

Healed extraction sockets (extraction carried out at least 3 months prior to recruitment)

Implant site free of infection

Systemically healthy patients or with controlled common systemic conditions

Adjacent teeth present both mesially and distally to the implant site

EXCLUSION CRITERIA

Pregnancy or intent to be pregnant over the next 12 months

Current smoking exceeding 10 cigarettes/day

Parafunctional habits/ excessive occlusal forces

Current orthodontic therapy

Uncontrolled hypertension (blood pressure over 160/100) or poorly-controlled diabetes (HbA1c>8%).

RECRUITMENT

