Potential participants will be approached by the study investigators and the scope and the procedures of the study will be thoroughly explained. Eligible individuals willing to participate will provide informed consent.

CONFIDENTIALITY OF THE DATA

Participants will be assigned individual study numbers that will be used to link all collected study data. All endpoint devices used for data collection will be password-protected and encrypted. PHI/PII data and all other study data will be stored in a secure, certified database. The following individuals/ institutions/ representatives will have access to the records: the Principal Investigator and co-investigators, the FDA, the Department of Human Health and Human Services, the Columbia University/New York Presbyterian Hospital, and the Institutional Review Board. Absolute confidentiality cannot be guaranteed because of potential need to share this information with the above parties. Only aggregate findings of this study will be published.

POTENTIAL CONFLICT OF INTEREST

The study is an investigator-initiated randomized controlled trial, where the Principal Investigator serves as the Sponsor-Investigator. The study is partially supported by a grant provided by the implant manufacturer (Nobel Biocare). None of the investigators have any financial interest in the company or have served as paid consultants.

LOCATION OF THE STUDY

All study procedures will take place at the Clinics for Post-doctoral Periodontics and Post-doctoral Prosthodontics, College of Dental Medicine, Columbia University Medical Center, Vanderbilt Clinic, 9th floor.

POTENTIAL RISKS

Study related risks: The overall success of dental implants exceeds 95%. Risks associated with the study are identical to those associated with surgical implant placement and include soreness, discomfort, pain, infection, nerve damage and implant failure.

Protection against risks: Implants will be placed and restored by post-doctoral residents who are proficient in the surgical and restorative aspects of implant dentistry, under faculty supervision. Patients will receive post-operative antibiotic and analgesic coverage, according to standard clinical protocol.

POTENTIAL BENEFITS

Patients will have the costs associated with implant surgery and provisional restoration waived, as these will be covered by funds provided by the implant manufacturer (NobelBiocare).

ALTERNATIVE THERAPIES

- 1) not to replace the missing tooth

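### Pain, infection and nerve damage are named as risks, but nothing in the plan records them or compares them by arm

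*Combined protocol and SAP*

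**What the plan says.** Under Potential Risks, the plan states that study risks match those of surgical implant placement and "include soreness, discomfort, pain, infection, nerve damage and implant failure". The protection paragraph that follows covers operator skill, supervision, and antibiotic and analgesic cover. It does not mention recording complications.

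The Study Design and Statistical Procedures Overview sets the outcomes: "The primary outcome of the study will be the radiographically assessed alveolar bone level change at the mesial and distal surface of the implant". It continues: "Secondary outcomes will include implant survival", followed by "volumetric soft tissue changes, peri-implant probing depth, and implant stability by resonance frequency analysis".

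The numbered list under Research procedures has five items: bone level on radiographs, soft tissue margin, probing depth, volumetric assessment from casts, and resonance frequency analysis. Item 3, for example, begins "Probing depth measurements around the implant (at 4 and 12 months" and concerns depth only.

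For the seven-month visit, Study Procedures says only that "patients in both treatment groups will return for a follow up visit to reinforce oral hygiene and will receive oral prophylaxis". Under Additional Data Collection, history forms serve to confirm eligibility and photographs serve documentation.

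**The concern.** The trial compares two loading protocols in a non-inferiority design, and the arms differ in what is done to the patient. One arm receives a temporary crown on the day of surgery, relieved from occlusal and laterotrusive contacts. The other has the implant uncovered through the mucosa at three months. Either step could plausibly change pain, infection or sensation, so a reader of the results will ask how often each occurred in each arm.

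The plan gives no means of answering. This is more than an unwritten analysis rule, because the observations themselves are not planned. Later analysis could not recover them in a form that is comparable between arms.

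**Working it through.** The main check sets each named risk against every place where the plan collects data.

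**Risks.** Six items are named. Soreness, discomfort and pain are one kind of harm, so there are four kinds: pain, infection, nerve damage and implant failure.

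**Collection points**
- Primary outcome: bone level change. It is not a record of any named risk.
- Secondary outcomes: survival matches implant failure. Soft tissue volume, probing depth and resonance frequency match none.
- Research procedures 1 to 5: no direct match. Resonance frequency measures stability and does not record failure. Bone level and probing depth are at most late, indirect signs of infection around the implant. Probing starts at four months.
- Post-operative visit at 1-2 weeks: soft tissue margin only.
- Seven-month visit: hygiene and prophylaxis only.
- Additional Data Collection: eligibility and documentation only.
- Power Calculations and Statistical Analysis: covers the primary and secondary outcomes, with no complication summary.

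**Result.** One of four kinds of harm has a planned by-arm outcome; three have none.

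**Timing of observation.** Study Procedures places the early visit of the one-stage arm 1-2 weeks after surgery. For the two-stage arm, Research procedures item 2 places it 1-2 weeks after uncovering, and no visit soon after placement is described. Recording at whatever visits each arm happens to have would therefore observe the arms unequally in the weeks after placement. The described follow-up time points common to both arms are 4, 7 and 12 months.

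**The plan's sample size.** With d = 0.5/0.6 = 0.8333, two-sided alpha 0.05 and power 0.80, the two-sample t-test needs 23.6 per arm, rounded up to 24, or 48 in total. This reproduces the stated figure, and the point does not alter it.

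**What recorded events could show.** The plan enrols 50. The allocation ratio is not stated, so 25 per arm with full follow-up is an assumption.
- Upper limit after 0 of 25, one-sided 95%: 1 − 0.05^(1/25) = 0.113. With 24 per arm it is 0.117.
- Upper limit after 0 of 25, two-sided 95%: 1 − 0.025^(1/25) = 0.137. With 24 per arm it is 0.142.
- Chance of at least one event in an arm, 1 − (1 − p)^25: 22% at p = 1%, 40% at 2%, 72% at 5% and 93% at 10%.
- Power of Fisher's exact test at two-sided 0.05: about 20% for 5% versus 20%, and about 55% for 5% versus 30%.

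The event rates are assumptions; the plan gives none for these complications.

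**The case against.** The strongest reply is that this is an ordinary reporting gap in a small trial whose claim concerns bone level. The plan announces no conclusion of equal safety, and 50 patients could not support one: even a fourfold infection rate would usually not be distinguished. That stands. It argues for descriptive counts, not for collecting nothing.

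Several stronger readings are tempting, and the documents do not support them.
- A reader might infer that no complication data will exist when the trial ends. The numbered list is not exhaustive: implant survival is missing from it, and so is insertion torque, a planned covariate. All procedures take place in one institution's clinics, whose charts may hold events. What the text shows is that no recording, extraction or comparison is planned.
- A reader might count five of six risks as uncovered. Three of those five are near-synonyms, so three kinds of harm is the fair count.
- A reader might take the statement on risks as a claim that the arms carry equal risk. It compares the study with ordinary implant placement, not one arm with the other.
- A reader might conclude that complications would go unnoticed or unmanaged. The gap lies in trial data; the plan says nothing to suggest that routine care would miss them.

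The objection that simply recording at every scheduled visit would bias the comparison is also right, and the fix has to meet it.

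**Conclusion.** The point holds as a gap in planned data collection. Pain, infection and nerve damage have no planned record and no by-arm comparison; implant failure is covered through survival. The change is worth making because it is cheap and the information cannot be rebuilt evenly afterwards.

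Its reach is limited. It leaves the primary analysis and the sample size of 48 untouched. The gain is a descriptive harm table, not evidence of comparable safety: an arm with no events would still be compatible with a true rate of up to about 11% (one-sided) or 14% (two-sided). Those limits rest on 1:1 allocation of 50 patients and complete follow-up, neither of which the plan states.

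**What to change.** Add an item to Research procedures: a complication record covering pain or soreness, infection or suppuration, altered sensation, and implant mobility or loss. For each, enter present or absent, onset date, action taken and resolution.

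Collect it in the same windows after implant placement in both arms: at any 1-2 week post-placement contact that both arms have, and at the common 4-, 7- and 12-month visits. At each, ask about all events since the last common time point. Record events after the three-month uncovering as well, with their onset date, so that they can be shown separately. State whether the two-stage arm has an early post-placement contact. If it does not, early events in both arms depend on recall at four months, and that limitation should be written down.

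Add patients with complications by arm as a descriptive secondary outcome, reported as counts with exact confidence intervals and no claim of equal safety. Noting bleeding during the probing already planned is optional.

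The cost is one form, a few minutes per visit, a protocol amendment, and a harm table that may look less favourable. No extra visit is needed if the windows above are used; an added early contact would be a further cost.
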